3.8.2. Analysis Visit Windows

Participant visits might not occur on protocol-specified days. Therefore, for the purpose of analysis, observations will be assigned to analysis windows.

The analysis windows for chemistry (except for SCr), hematology and coagulation laboratory tests are provided in Table 3-1. CCI

Table 3-1. Analysis Visit Windows for Chemistry (Except for SCr), Hematology, and Coagulation Laboratory Tests

Nominal Visit	Nominal Study Day	Visit Window Study Day	
		Lower Limit	Upper Limit
Baseline	1	(none)	1 (Pre Dose)
Day 3	3	1 (Post Dose)	3
Day 5	5	4	6
Day 8	8	7	10
Day 12	12	11	14
Day 16	16	15	18
Day 20	20	19	22
Day 24	24	23	26
Day 29	29	27	44

The 8-point ordinal scale will be collected daily from Day 1 through Day 29 or discharge, whichever is earlier, as well as at the Day 29 and Day 60 phone follow-up. The analysis visit window will coincide with each study day up to Day 44 with 1 exception: a Day 1 postdose record will be mapped to Analysis Day 2 visit (the 8-point ordinal scale will be collected twice on Day 1: predose and the worst score on Day 1 post-dose). If any additional records are collected after Day 44, the analysis window is provided in [Table 3-3](#).

Table 3-3. Analysis Visit Window for 8-Point Ordinal Scale Collected after Day 44

Nominal Visit	Nominal Study Day	Visit Window Study Day	
		Lower Limit	Upper Limit
Day 60	60	45	(none)

Vital signs, and SCr will be collected daily from Day 1 through Day 29 or discharge, whichever is earlier, per protocol; therefore, the analysis visit window will coincide with each study day up to Day 29 with 1 exception: a Day 1 postdose record will be mapped to Analysis Day 2 visit.

3.8.3. Selection of Data in the Event of Multiple Records in an Analysis Visit Window

Depending on the statistical analysis method, single values may be required for each analysis window. For example, change from baseline by visit usually requires a single value, whereas a time-to-event analysis would use all data regardless of analysis window.

If multiple valid, nonmissing measurements exist in an analysis window, records will be chosen based on the following rules if a single value is needed:

- For baseline, the last nonmissing value on or prior to the first dosing date (and time, if available) of study drug will be selected, unless specified differently. If there are multiple records with the same time or no time recorded on the same day, the baseline value will be selected as follows:

— For continuous data:

- CCI [REDACTED]
- For other continuous data, the average of the measurements will be taken.

— For categorical data:

- For SARS-CoV-2 infection status, the highest severity (ie, a positive PCR result) will be selected.
- For other categorical data, the lowest severity will be selected.

For the 8-point ordinal scale, only Screening and Day 1 predose values will be considered for baseline value selection.

[REDACTED]

[REDACTED]

[REDACTED]

CC
[Redacted]

[Redacted]

[Redacted]

[Redacted]

[Redacted]

[Redacted]

In an analysis window (including baseline window), if both central lab and local lab results are available, then central lab results will be used for record selection instead of local lab results; local lab results will only be used for record selection if central lab results are missing.

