Appendix 3. Study Procedures Table

	Screening	Baseline/ Day 1	Day 2	Day 3	Day 4	Day 5	Day 6	Day 7	Day 8	Day 9, 10, 11	Day 12	Day 13	Day 14	Day 15	Day 16	Day 17, 18, 19	Day 20	Day 21	Day 22, 23	Day 24	Day 25, 26, 27, 28	Day 29*	Day 29 and Day 60 Phone Follow-up Visits (+ 5 days)
Written Informed Consent	X																						
Inclusion/Exclusion Criteria	X																						
Focused Medical History, including SCr values ^a	X																						
Documentation of SARS-CoV-2 Infection ^b	X																						
Complete Physical Examination	X																						
Height	X																						
Weight	X																						
Vital Signs ^c	X	X	X	X	X	X	X	X	X	X	X	X	X	X	X	X	X	X	X	X	X	X	X
Respiratory Status ^d	X	X	X	X	X	X	X	X	X	X	X	X	X	X	X	X	X	X	X	X	X	X	X
Invasive Mechanical Ventilation ^g	X	X	X	X	X	X	X	X	X	X	X	X	X	X	X	X	X	X	X	X	X	X	X
Pulmonary Radiographic Imaging ^e	X																						
8-Point Ordinal Scale ^f	X	X	X	X	X	X	X	X	X	X	X	X	X	X	X	X	X	X	X	X	X	X	X
Pregnancy Test ^h	X																						
Chemistry ^{h,r}	X	X		X		X			X		X				X		X			X		X	
Hematology ^{h,r}	X	X		X		X			X		X				X		X			X		X	

	Screening	Baseline/ Day 1	Day 2	Day 3	Day 4	Day 5	Day 6	Day 7	Day 8	Day 9, 10, 11	Day 12	Day 13	Day 14	Day 15	Day 16	Day 17, 18, 19	Day 20	Day 21	Day 22, 23	Day 24	Day 25, 26, 27, 28	Day 29*	Day 29 and Day 60 Phone Follow-up Visits (+ 5 days)	
Coagulation ^{1,f}	X	X		X		X			X		X				X		X			X		X		
Serum Creatinine ^{r,s}	X	X	X	X	X	X	X	X	X	X	X	X	X	X	X	X	X	X	X	X	X	X	X	
Urinalysis ^l	X																							
RRT Assessment ^k	X	X	X	X	X	X	X	X	X	X	X	X	X	X	X	X	X	X	X	X	X	X	X	X
Virologic Testing ^l		X		X		X		X					X					X				X		

[figure not shown]
CCI

CCI

CCI

Investigational Drug Dosing		X	X	X	X	X																		
Adverse Events	X	X	X	X	X	X	X	X	X	X	X	X	X	X	X	X	X	X	X	X	X	X	X	X
Concomitant Medications	X	X	X	X	X	X	X	X	X	X	X	X	X	X	X	X	X	X	X	X	X	X	X	X
Mortality																							X	
Hospital Readmission Rate																							X	

* All assessments to be completed through Day 29, or until discharge, whichever is earlier. If participant is discharged prior to Day 29, a phone follow-up is to be completed at Day 29 and Day 60.

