3.8. Analysis Visit Windows

3.8.1. Definition of Study Day

Study day will be calculated from the first dosing date of study drug and derived as follows:

- For assessment dates on or after the first dosing date: Assessment Date – First Dosing Date + 1
- For assessment dates prior to the first dosing date: Assessment Date – First Dosing Date

Therefore, Study Day 1 is the day of first dose of study drug administration.

Last Dose Date is defined as the maximum, nonmissing, nonzero dose end date of treatment recorded on the Study Drug Administration eCRF form with “Study Drug Permanently Withdrawn” box checked for participants who prematurely discontinued or completed study drug according to the Study Drug Completion eCRF.

Last dose date is not expected to be missing. However, if last dose date is missing, it will be imputed using the maximum of non-missing, non-zero dose, study drug start and stop dates.

Last Study Date is the latest of study drug start dates and end dates, the in-person or phone visit dates, the vital sign and the laboratory collection dates, including the Day 60 phone follow-up visit date. For participants who died during the study, the death date will be the Last Study Date. For participants who died after completing the study or after prematurely discontinuing the study, the death date will not be considered for the Last Study Date.

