6.2.1. Analysis of Secondary Efficacy Endpoints

The key α -controlled secondary endpoint of all-cause mortality through Day 29 will be analyzed in a similar manner to the primary endpoint.

Initiation of IMV through Day 29 and time to recovery through Day 29 will also be analyzed in a similar manner to the primary endpoint except that a competing risk analysis approach will be used with death as the competing risk.

For analysis on time to recovery through Day 29, two sets of analyses will be conducted:

(1) Time to recovery through Day 29, in which the first recovery without further worsening in the ordinal scale score (ie, a score of > 4) by Day 29 will be considered an event; (2) Time to recovery through Day 29, in which the first recovery (regardless of further worsening or not) will be considered an event.

The clinical status assessed by the 8-point ordinal scale at Day 15 and Day 29 will be analyzed using a proportional odds model including treatment as the independent variable. Two models will be explored; one with baseline score as a continuous covariate and one without baseline score as a covariate. The odds ratio and 95% CI will be provided. The percentage of participants in each category will be summarized by treatment group. The assumption of odds proportionality will be assessed using a score test and reported. Clinical status by study day and change from baseline up to Day 29 will also be summarized by treatment group.

For participants without ESKD at baseline, the number of RRT-free days will be calculated between date of first dose and Day 29. The number of RRT-free days will be calculated as the number of full days from Day 1 to Day 29 that the participant was alive and did not receive RRT. The number of RRT-free days will be summarized by treatment group, and compared between treatment groups using Wilcoxon rank sum test.

The proportion of participants with recovery through Day 29 will be summarized by treatment group, and compared between treatment groups using the CMH test stratified by randomization strata. Similar for time to recovery analysis, two sets of analyses will be conducted: (1) The proportion of participants with recovery through Day 29, in which recoveries without further worsening by Day 29 is considered; (2) The proportion of participants with recovery through Day 29, in which recoveries regardless of worsening status by Day 29 is considered.

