The key α -controlled secondary endpoint of all-cause mortality through Day 29 will also be analyzed for each of the subgroups defined in Section 3.4. Other secondary endpoints may also be analyzed for each of the stratification factor subgroups.

For time to event analysis of secondary endpoints, participants with missing outcomes due to premature discontinuation of the study on or prior to Day 29 will be censored at the date of last known status for that endpoint.

Clinical status assessed by the 8-point ordinal scale will be derived by combining the available death, hospital discharge alive and ordinal scale assessment reported by the site, where death supersedes discharge alive and discharge alive supersedes the ordinal scale score reported by the site.

Sites were instructed to report the worst ordinal scale category for each day. Therefore, the ordinal scale result on the day the participant was discharged alive does not necessarily reflect Not hospitalized. The definition of clinical status based on the 8-point ordinal scale is defined as follows:

- If a participant dies on or prior to Day 29, clinical status on the day of death and all subsequent days through Day 29 will be set as 8 (death)
- If a participant is discharged alive on or prior to Day 29, clinical status on the day of discharge alive will be set to 2 (not hospitalized, limitation on activities and/or requiring home oxygen), which is the worst score for a non-hospitalized participant
- If a participant is discharged alive and subsequently re-admitted on or prior to Day 29, and the 8-point ordinal score is not reported on the day of re-admission, the clinical status on the day of the re-admission will be imputed to 7 (hospitalized, on IMV or ECMO), which is the worst score for a hospitalized participant
- For other missing ordinal scores from Day 2 through Day 29, the clinical status will be imputed using the previous day's score (either reported score or imputed score as applicable)

The FAS will be the primary analysis set for the secondary efficacy endpoints.

CCI

[REDACTED]

- [REDACTED]
- [REDACTED]
- [REDACTED]
- [REDACTED]
- [REDACTED]
- [REDACTED]
- [REDACTED]
- [REDACTED]
- [REDACTED]
- [REDACTED]
- [REDACTED]

CCI

CCI

CCI

CCI

CCI

CCI [Redacted]

CCI [Redacted]

[Redacted]

[Redacted]

[Redacted]

[Redacted]

[Redacted]

[Redacted]

[Redacted]

[Redacted]

[Redacted]

[Redacted]

[Redacted]

CCI

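### A Day 29 phone ordinal score dated Day 30 to 34, inside the allowed +5 days, is not used for Day 29; an observed category 1 is then analysed as a carried-forward 2

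*SAP*

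**What the plan says.** - **Collection after discharge.** Protocol 6.10 collects the ordinal score after discharge only at the Day 29 and Day 60 phone follow-ups. The column heading in Protocol Appendix 3, repeated in SAP Appendix 1, is "Day 29 and Day 60 Phone Follow-up Visits (+ 5 days" (closing bracket omitted here). A compliant Day 29 call can therefore fall on Day 29 to Day 34.
- **Study day.** SAP 3.8.1: "Study day will be calculated from the first dosing date of study drug", using the date of the assessment and not the nominal visit.
- **Windows.** SAP 3.8.2 on the ordinal scale: "The analysis visit window will coincide with each study day up to Day 44 with 1 exception". Later records fall under Table 3-3, "Analysis Visit Window for 8-Point Ordinal Scale Collected after Day 44", which assigns everything from Day 45 onward to Day 60.
- **Discharge and missing scores.** SAP 6.2.1: "clinical status on the day of discharge alive will be set to 2". It continues: "For other missing ordinal scores from Day 2 through Day 29, the clinical status will be imputed using the previous" day's score, whether that score was reported or itself imputed. A general sentence in the same section says "discharge alive supersedes the ordinal scale score reported by the site". Deaths are set to 8 and readmissions have a separate rule.
- **Use.** Clinical status at Day 29 is a named secondary endpoint without alpha control. It is analysed by a proportional odds model, and "The percentage of participants in each category will be summarized by treatment group".

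**The concern.** The Day 29 call exists to supply Day 29 status for people who have gone home. The SAP gives the Day 60 ordinal score a wide window, and Table 3-1 gives the Day 29 chemistry, hematology and coagulation tests a window of Days 27 to 44. The Day 29 ordinal call has no tolerance at all. A call that is on time by the protocol but one or more days after Day 29 is set aside, and an imputed 2 takes its place.

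At stake is the split between category 1 (no limitation) and category 2 (limitation or home oxygen) in the Day 29 table, the proportional odds model and the by-day summaries. That split would depend partly on when sites place their calls.

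**Working it through.** **Step 1: trace the rules.** Take a participant discharged alive before Day 29, not readmitted, alive at Day 29, with category 1 observed at the call. Assume that the score carries the call date. Discharge days 6, 14 and 28 give the same result.

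| Call dated | Analysis day of the score | Day 29 value analysed |
|---|---|---|
| Day 29 | 29 | 1 (observed) |
| Day 30, 31, 32, 33 or 34 | same as call day | 2 (carried from discharge) |

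An observed 2 stays 2. If the score is attributed to the day before the call, a Day 30 call fills Day 29 and only Days 31 to 34 are affected. If the form dates the score as Day 29 status, nothing is lost.

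**Step 2: effect on the category table.** Let L be the share of calls that are late. Assume that lateness is unrelated to category and that status does not change between Day 29 and the call. Then

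reported category 1 share = (1 − L) × category 1 share observed by phone,

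and category 2 gains the difference. With an assumed 30% observed by phone:

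- L = 25%: 0.75 × 30% = 22.5%
- L = 50%: 0.50 × 30% = 15%
- L = 5/6 (calls spread evenly over the six days 29 to 34): 1/6 × 30% = 5%

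The replaced scores are an upper bound on the category 1 scores that were right for Day 29: someone at 2 on Day 29 and 1 on Day 33 is correctly analysed as 2.

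**Step 3: effect on the model.** The documents give no late-call rate, no category distribution and no assumed effect for this endpoint, so every input is an assumption:

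- Placebo Day 29 distribution, categories 1 to 8: 30/30/2/3/4/3/7/21%.
- Allocation 2:1. N = 550 (183 and 367) is near the ceiling, because SAP 2.2 says enrollment stopped before 50% of plan and 1116 / 2 = 558. N = 250 (83 and 167) is a smaller case.
- (A) Common odds ratio 1.5 at every cut. (B) Odds ratio 1.5 at the other cuts, but the same 1:2 ratio in both arms.
- Equal lateness in both arms and no change of status before the call.
- Tie-corrected Wilcoxon rank test, equivalent to the proportional odds score test; two-sided 0.05; 100,000 simulated trials per scenario.

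| Share late | 0 | 25% | 50% | 5/6 |
|---|---|---|---|---|
| Power, N = 550, A | 70% | 66% | 62% | 60% |
| Power, N = 550, B | 49% | 50% | 52% | 56% |
| Power, N = 250, A | 39% | 36% | 33% | 32% |
| Power, N = 250, B | 26% | 26% | 27% | 30% |
| Fitted odds ratio, A | 1.50 | 1.47 | 1.46 | 1.48 |
| Fitted odds ratio, B | 1.38 | 1.38 | 1.40 | 1.46 |

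Other placebo splits of categories 1/2, N = 550, at 0, 50% and 5/6 late:

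- 15/45: A 68%, 63%, 61%; B 52%, 55%, 58%.
- 45/15: A 67%, 57%, 57%; B 52%, 50%, 55%.

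Type I error at 0, 50% and 5/6 late is 0.049, 0.050 and 0.051.

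**Step 4: other endpoints.** Recovery is category 1, 2 or 3, so moving a 1 to a 2 changes no recovery outcome. Death and invasive ventilation do not use the split.

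**The case against.** **The dating premise is not stated.** Protocol 6.9 treats the scale as describing a given study day and separates the day of collection from the day scored. A late call could therefore be recorded as Day 29 status, and neither document shows the form. This stands: the point is conditional, and the SAP should settle the condition.

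**A score from Day 30 to 34 is not Day 29 truth.** This also stands. The figures above give the largest loss for each late rate.

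**Keeping each score on its own day may be a deliberate, conservative choice.** SAP 6.2.1 calls 2 the worst score for a non-hospitalized participant. At Day 15, when no phone score is scheduled, discharged participants who are not readmitted are all carried at 2. That is a fair account of the default where nothing was collected. It is weaker at Day 29, where a follow-up was scheduled to obtain the score.

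**Redaction.** Parts of SAP 3.8.3 and a programming item in SAP Appendix 2 are blacked out. The visible 3.8.3 heading concerns several records within one window, and item 31 of the appendix covers late vital signs, SCr and PCR only. A hidden cross-day rule is unlikely but cannot be excluded.

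**Stronger readings that the documents do not support.** A reader might infer that the Day 29 comparison is biased against remdesivir or loses power. With equal lateness, as blinding leads one to expect, power moves in either direction and the test stays valid. A reader might also infer that every post-discharge phone score is discarded, because discharge alive supersedes the site score. The itemised rule assigns the 2 to the day of discharge only. The general sentence carries no such limit, which is a reason to clarify it and not proof of that reading.

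**Conclusion.** The point holds as a minor, conditional one. If the phone score carries the call date, SAP 3.8.1, 3.8.2 and 6.2.1 together replace an observed category 1 from an in-window call dated Day 30 to 34 (or 31 to 34) with a carried-forward 2. No readable passage maps it back.

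The reported category 1 share falls to at least (1 − L) times the share that truly belongs to Day 29, on the assumption that hardly anyone moves from 1 to 2 before the call. L is unknown; if no call is late, nothing changes. In the base case with equal lateness, the fitted odds ratio moved by at most 0.08 (1.38 to 1.46). Across all the splits tried, power moved by between −10 and +7 percentage points. These are illustrations on assumed inputs and not estimates for this trial. The effect stays within the category 1/2 split at Day 29.

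**What to change.** **SAP 3.8.2.** When no ordinal score is dated Day 29, map the Day 29 phone-follow-up score dated up to Day 34 to Analysis Day 29. State which day the phone score describes. If the participant died or was readmitted after Day 29 and before the call, keep the carried-forward value, because Day 29 status is then known to be alive and not hospitalized.

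**SAP 6.2.1.** State that the rule giving discharge precedence over the site's score applies to the day of discharge only. State that carry-forward is used only when no in-window phone score exists or the exception above applies. The existing death and readmission rules stay. Report the carried-forward version as a sensitivity analysis.

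**Cost.** One windowing rule with a dating statement, two clarifying sentences, the matching program and one extra model run; no new data. It should be settled before unblinding, when SAP section 1 says that the plan is finalized.

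**Downside to state in the SAP.** The mapped score may describe status up to 5 days after Day 29. Later improvement is mapped back while later death or readmission is not, so the rule may slightly favour category 1, equally in both arms under blinding.

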3.9. Change from Protocol-Specified General Considerations

The multiplicity adjustment specified in the protocol Section 8.7 was changed because the interim analysis planned after 50% of participants completed the Day 29 assessment was not performed due to the stop of study enrollment prior to reaching 50% of planned enrollment. As there was no interim analysis, there was no alpha spent and the final analysis is planned at the 0.05 significance level (see Section 2.3).

4. PARTICIPANT DISPOSITION

4.1. Participant Enrollment and Disposition

A table of key study dates will be provided, including first participant screened, first participant enrolled, last participant enrolled, last participant last visit for the primary endpoint, and last participant last visit.

The number and percentage of participants enrolled at each investigator site and country will be summarized by treatment group and overall. The denominator for this calculation will be the number of participants analyzed for that column.

A similar enrollment table will be provided by randomization stratum. The denominator for the percentage of participants in the stratum will be the total number of participants in the Safety Analysis Set. If there are discrepancies in the value used for stratification assignment between the IXRS and the clinical database, the value collected in the clinical database will be used for the summary. A listing of participants with discrepancies in the value used for stratification assignment between the IXRS and the clinical database at the time of data finalization will be provided.

A summary of participant disposition will be provided by treatment group and overall for all screened participants. This summary will include the number of participants screened, screen failure participants who were not randomized, participants who met all eligibility criteria but were not randomized, participants randomized, participants randomized but never treated, participants in the Safety Analysis Set, and Full Analysis Set (FAS).

In addition, the number and percentage of the participants in the following categories will be summarized:

- Completed study drug
- Did not complete study drug with reasons for premature discontinuation of study drug
- Completed study
- Did not complete study with reasons for premature discontinuation of study

The denominator for the percentages of participants in each category will be the number of participants in the Safety Analysis Set corresponding to that column.

No inferential statistics will be generated. A data listing of reasons for premature study drug/study discontinuation will be provided.

A summary of analysis sets will also be provided by treatment group and overall.

4.2. Extent of Study Drug Exposure

Number of doses received will be summarized by treatment group for the Safety Analysis Set.

4.3. Protocol Deviations

A listing will be provided for all randomized participants who violated at least 1 inclusion or exclusion criterion. The listing will include the criteria not met.

Protocol deviations occurring after participants entered the study are documented during routine monitoring. The number and percentage of participants with important protocol deviations and the total number of important protocol deviations by deviation reason (eg, violation of select inclusion/exclusion criteria) will be summarized by treatment group for the FAS. A by-participant listing will be provided for those participants with important protocol deviations.

